### 6.2 PERMITTED MEDICATIONS

Subjects on therapy for their uveitis will not be asked to stop their usual medications, rather they will add TRS01 QID to their current regimen. Therapy considered necessary for the subject's welfare that does not interfere with the evaluation of the study medication will be permitted to be given at the discretion of the Principal Investigator.

The decision to administer a prohibited medication or treatment would be taken with the safety of the subject as the primary consideration. Whenever possible, the Tarsius Medical Director will be notified before any prohibited medications or treatments are administered. The Tarsius Medical Monitor should also be contacted if the permissibility of a specific medication or treatment is in question.

Any subject placed on rescue therapy will discontinue use of the IP and continue study participation through Visit 7.

Subjects on rescue therapy due to lack of efficacy should not be withdrawn from the study, but rather followed through the end of the study.

Rescued subjects experiencing an AE at the time of rescue will be followed through stabilization or resolution of the AE or the end of the study (whichever comes first).

The following medications are also specifically permitted during the trial:

- Glaucoma eye drops with the exclusion of Prostaglandins. Note: subjects may be treated with up to two glaucoma eye drops in the study eye. Anti-glaucoma eye drops should be [REDACTED] before the investigational product dosing.
- Mydriatic agents
- Use of PRN artificial tears up to twice a day
- [REDACTED]  
[REDACTED]

- [REDACTED]
- [REDACTED]
- [REDACTED]
- [REDACTED]

**The above medications, if used at the onset of the trial, must not be discontinued during the course of the trial and the dosing and regimen should remain stable through Visit 5 (end of IP treatment period).**

### 6.3 RESCUE MEDICATION USE

Rescue medications will be administered in cases detailed in [section 7.2.2](#). Rescue therapy will be defined as any treatment (above the permitted dosages outlined in the eligibility criteria and in Section 6.2) that would have a therapeutic effect on inflammation in the anterior segment, other than the IP (e.g., systemic treatment with an immunosuppressant agent, ocular injection of steroids, or topical corticosteroids in the study eye), regardless of the purpose of administration and whether it was recorded as a rescue therapy on the eCRF.

The addition or increase in systemic immunosuppressive therapy (e.g., methotrexate, cyclosporine, cyclophosphamide, chlorambucil, mycophenolate mofetil, tacrolimus, azathioprine, or adalimumab) or other therapy considered as a rescue therapy, would be administered based on the Investigator's best judgment and only after discussion with Tarsius' Medical Director.

#### **6.4 MEDICATIONS NOT PERMITTED**

Use of the following medications are not permitted either during the study or for the timeframes, frequency or dose levels defined here:

1. Intravitreal or periocular steroids in the study eye within 90 days of Visit 1.
2. Any intravitreal injection within 30 days of Visit 1.
3. Topical ocular therapy with steroids more than BID in the study eye, throughout the IP treatment period.
4. Treatment with systemic steroids  $>10\text{mg/day}$ , throughout the IP treatment period.
5. Any topical ophthalmic medications (either eye) other than medications specifically allowed as part of the trial, throughout the IP treatment period. Note: Use of PRN artificial tears up to twice a day (BID) is allowed and should not be dosed within 10 minutes of investigational product dosing. Further, changes in the dosing of cycloplegics as needed during the study is allowed.
6. Other investigational drugs or or investigational medical device within 60 days prior to Visit 1.

#### **6.5 TREATMENT COMPLIANCE**

In order to obtain reliable safety and efficacy data, it is critical that each subject comply with the dosing schedule specified in the protocol.

Subjects will be instructed to record administration information from Day 1 and for the duration of the study in a dosing diary.

## 7 SAFETY AND EFFICACY VARIABLES

### 7.1 SAFETY VARIABLE

Incidence and severity of treatment-related AEs and SAEs, both systemic and ocular reported adverse events.

### 7.2 SAFETY VARIABLES

Safety measures include AEs/SAEs and clinical assessments from the slit-lamp biomicroscopy findings, IOP, and dilated ophthalmoscopy findings.

AEs and ocular safety measures to be collected in this study are listed in [Table 3](#).

**TABLE 3: OCULAR SAFETY MEASURES**

Safety Measure	Note
Slit-lamp biomicroscopy: Lid hyperemia, lid edema, conjunctival hyperemia, chemosis, corneal edema, conjunctival discharge/exudate	The status of each of these biomicroscopy parameters will be rated as 0 = None, 1 = Mild, 2 = Moderate, or 3 = Severe. For each abnormal record, the clinical significance (Clinically Significant or Not Clinically Significant) will also be determined. Slit-lamp biomicroscopy will be performed at all study visits.
Intraocular pressure	The IOP measurements will be performed by Goldmann applanation tonometry with a single measurement. IOP pressure recorded in mmHg (e.g., 18 mmHg). IOP measurements will be performed at all study visits,
Dilated Ophthalmoscopy: Vitreous haze, retina vessels, macula, optic nerve, cup/disc ratio.	The status of the macula, vessels and optic nerve will be determined as Normal or Abnormal. The cup/disc ratio will be recorded with two decimal points (e.g., 0.80). Dilated ophthalmoscopy will be performed at all visits.
BCVA	The visual acuity test is used via a standardized ETDRS chart.

These ocular safety measures will be summarized using descriptive statistics. For continuous ocular safety measures, changes from Baseline (Day 1/Visit 1) variables will also be summarized descriptively. Safety parameters of interest include a change from baseline to each visit in ocular signs such as corneal/conjunctival tolerability, IOP measurements.

### 7.2.1 Adverse Events

Adverse events will be collected for subjects following signing of the ICF through the end of the study. The information will include at least a description of the event, onset date, and resolution date, as well as seriousness, severity and relation to study medication (as determined by the Investigator), location (right eye [OD], left eye [OS], both eyes [OU] or other), action taken, and outcome. All AEs will be coded using the Medical Dictionary for Regulatory Activities (MedDRA) dictionary, current version. Ocular and non-ocular AEs will be summarized separately.

*Suspected adverse reactions* (SARs), also known as adverse drug reactions or suspected adverse drug reactions, are AEs considered by the Investigator to be related to the study medication and included in the Investigator's Brochure.

An AE will be considered as an *ocular AE* if the Investigator selects 'OD', 'OS', or 'OU' for the AE eCRF field "Eye(s) affected".

Any AE that causes loss of vision of 15 or more letters (i.e., 3 lines) should be recorded as a serious adverse event (SAE). Examples include endophthalmitis, retinal vascular occlusion, retinal detachment involving the macula/fovea, etc. AEs that cause loss of 15 or more letters (i.e., 3 lines) that are expected to resolve should not be recorded as an SAE. Examples include corneal edema, corneal abrasion, cystoid macular edema or other conditions that are known to affect vision but expected to resolve and not result in a permanent impact on vision.

### 7.2.2 Criteria for Rescue Therapy

Rescue therapy will be offered if one or more of the following rescue criteria are met and a rescue therapy treatment plan is discussed with the Tarsius Medical Officer:

- If visual acuity in the study eye decreases by >2 lines compared to baseline, which in the opinion of the investigator, is due to non-infectious anterior uveitis.
- [REDACTED]

If rescue therapy is initiated, the subject will be instructed to discontinue IP. The choice of rescue therapy will be at the discretion of the Investigator. If rescue therapy is administered, the generic name, indication, route of administration, frequency, dose, start date, and stop date (if applicable) will be recorded on the eCRF. In addition, if other local therapy (i.e., periocular or intravitreal corticosteroids) is administered in the non-study eye, then the generic name,

indication, route of administration, frequency, dose, start date and end date (if applicable) would also be recorded on the eCRF.

Any medication administered on Visit 5 (Day 28) after the subject has exited the study will not be considered as rescue therapy.

If possible, during the visit where rescue therapy is initiated, Macular OCT should be performed for the study eye.

### 7.2.3 Other Safety Variables

Other safety measures are discussed in [section 7.2](#) above.

## 7.3 ADVERSE EVENT DEFINITIONS

**Adverse Event (AE):** Any untoward medical occurrence associated with the use of an investigational product in humans, whether or not considered drug related.

**Adverse Reaction (AR):** any AE caused by a drug. Adverse reactions are a subset of all suspected adverse reactions where there is reason to conclude that the drug caused the event.

**Suspected Adverse Reaction (SAR):**

Any AE for which there is a reasonable possibility that the drug caused the AE. For the purposes of IND safety reporting, “reasonable possibility” means there is evidence to suggest a causal relationship between the drug and the AE. A SAR implies a lesser degree of certainty about causality than adverse reaction, which means any AE caused by a drug.

**Unexpected:** An AE or SAR is considered “unexpected” if it is not listed in the Investigator’s Brochure or is not listed at the specificity or severity that has been observed; or, if an Investigator’s Brochure is not required or available, is not consistent with the risk information described in the general investigational plan or elsewhere in the current application.

**Life-threatening:** An AE or SAR is considered “life-threatening” if, in the view of either the Investigator or sponsor, its occurrence places the patient or subject at immediate risk of death. It does not include an AE or suspected adverse reaction that, had it occurred in a more severe form, might have caused death.

**A SERIOUS ADVERSE EVENT (SAE)** is any AE or suspected adverse reaction occurring at any dose that:

- Results in death.
- Is life-threatening.

- Results in a persistent or significant incapacity or substantial disruption of the ability to conduct normal life functions.
- Requires inpatient hospitalization.
- Prolongs inpatient hospitalization.
- Is a congenital anomaly/birth defect.
- Is a significant medical event (i.e., one that may jeopardize the subject or may require intervention to prevent one or more of the other outcomes listed above).

**A NON-SERIOUS ADVERSE EVENT** is any AE that does not meet the definitions for SAEs as described above.

Each **AE** will be classified as **SERIOUS or NON-SERIOUS** using the definitions provided above.

The **SEVERITY** of each AE will be classified as **MILD, MODERATE, or SEVERE**. The Investigator will review each event and assess its **RELATIONSHIP** to use of investigational product (unrelated, probably, definitely). The AE will be assessed using the following definitions:

**Unrelated:**

- Event occurring before dosing.
- Event easily explained by uveitis status.
- Event or intercurrent illness due wholly to factors other than investigational product use.

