## 1 INTRODUCTION

Uveitis refers to a broad spectrum of ocular inflammatory diseases which are associated with both systemic infectious and non-infectious conditions. Non-infectious uveitis, a potentially blinding condition that is the fifth leading cause of visual loss in the developed world (third leading cause of preventable blindness), has been estimated to account for 10% of all visual impairment in the western world and 10–15% of cases of total blindness [Nussenblatt, 1990; Merida et al., 2015].

The inflammation associated with uveitis affects the uvea of the eye (iris, ciliary body and choroid) and it is characterized by an inflammatory process that may be acute, recurrent, chronic or acute-on-chronic. Untreated, recurrent bouts of uveitis eventually lead to tissue destruction from direct inflammation or from complications such as cataract, glaucoma and macular edema. Clinically, uveitis manifestations include pain, blurry vision, conjunctival hyperemia, anterior chamber cells, anterior chamber flare, fibrin deposition and corneal endothelial inflammatory precipitates.

Uveitis may affect either the anterior or the posterior segment or in the case of panuveitis, it affects the entire eye. Anterior uveitis, which specifically refers to uveitis in the anterior segment of the eye, is the most common and accounts for approximately 80% of non-infectious uveitis cases in the United States [Thorne et al., 2016].

The present clinical trial evaluates the treatment of non-infectious anterior uveitis with TRS01.

Topical corticosteroids represent first line treatment for both non-infectious anterior uveitis and postoperative inflammation [Kim et al., 2019]. The side effects associated with steroid use significantly limit prolonged treatment. The most common adverse effects of ocular steroids are cataract and elevated intraocular pressure (IOP) which can lead to steroid related glaucoma.

Given the limitations of steroid treatment, there is an unmet medical need for an effective anti-inflammatory drug that does not have an IOP-elevating effect or cause the formation of cataracts. Tarsius Pharma, Ltd. has developed a novel therapeutic approach for local prevention and treatment of ophthalmic inflammatory diseases. [REDACTED]

TRS is the active drug substance of TRS01 which is an [REDACTED] drug product candidate developed for topical ocular administration (eye drops). Pre-clinical studies have demonstrated the safety and tolerability of TRS01.

[REDACTED]

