**Probable:**

- Reasonable temporal relationship with investigational product use.
- Likely to be known reaction to agent or chemical group, or predicted by known pharmacology.
- Event cannot easily be explained by subject's clinical state or other factors.

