#### 9.1.2 Analysis of Safety

Analysis of safety data will be presented for all subjects. AEs will be coded using Medical Dictionary for Regulatory Activities (MedDRA, most current version add in version once finalized) and categorized by system organ class using preferred terms. Treatment emergent AEs will be listed by study group. Treatment related AEs will be tabulated by study group and will be reported by incidence (both number of events and number of subjects) with respect to their intensity and relationship to the IP. Ophthalmoscopy findings will be summarized descriptively. IOP measurements, VA, and slit-lamp biomicroscopy assessments will be summarized as safety outcomes.

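### Section 7.3 lets a uveitis-like event be rated Unrelated even when a drug contribution is plausible, so the treatment-related AE table can under-count drug-induced worsening

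*Combined protocol and SAP*

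**What the plan says.** Section 7.3 gives three causality levels, and Section 7.4 repeats them: Unrelated, Probable and Definite. Unrelated has three grounds: onset before dosing, "Event easily explained by uveitis status", and "Event or intercurrent illness due wholly to factors other than investigational product use". Probable includes the condition "Event cannot easily be explained by subject's clinical state or other factors". Definite has the same condition without the word easily.

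Two other places use a lower threshold. Section 7.3 defines a suspected adverse reaction by a reasonable possibility that the drug caused the event. The note closing Section 7.5 applies to unexpected serious events judged related, or possibly so, and the scale has no such level.

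The Introduction says "Clinically, uveitis manifestations include pain, blurry vision, conjunctival hyperemia, anterior chamber cells, anterior chamber flare", and goes on to fibrin and corneal precipitates. It adds that untreated, recurrent disease can lead to "complications such as cataract, glaucoma and macular edema".

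On analysis, Section 3.1 makes the incidence and severity of both treatment-emergent and treatment-related AEs the primary safety parameter, while Section 7.1 names only treatment-related AEs and SAEs. Section 9.1.2 has treatment-emergent AEs listed, and then states "Treatment related AEs will be tabulated by study group", with incidence, intensity and relationship. Both arms receive TRS01 (Section 3.3), and no vehicle arm is described.

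**The concern.** Every subject enters with active anterior uveitis, so a disease explanation is available for many ocular complaints. An irritant or pro-inflammatory drop would produce some of the same complaints. If the disease explanation is enough for Unrelated, whatever the timing and whatever the change from Visit 1, a drug effect that looks like uveitis can drop out of the treatment-related count.

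That count carries weight here. Safety and tolerability is the primary objective. With two active arms, an effect common to both concentrations cannot appear as a difference between them, so attributing it to the drug rests largely on the investigator's causality rating.

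**Working it through.** No figure in the plan depends on this rule, so there is nothing to reproduce. The check has three parts.

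**1. Trace an event through the scale.** Take a study-eye event that begins or worsens after the first dose, that uveitis could readily explain, and to which the drug may have contributed.

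- Unrelated: the uveitis ground is met. The next ground requires a cause that lies wholly outside the product. The uveitis ground has no such limit, so a partial drug contribution does not block it.
- Probable: fails, because the clinical state easily explains the event.
- Definite: fails, because the clinical state explains the event.
- Suspected adverse reaction: can be met, because a reasonable possibility is enough.

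The same event can therefore be a suspected adverse reaction and Unrelated. This reads the grounds under Unrelated as alternatives (an event before dosing cannot sensibly need the other two as well) and the conditions under Probable and Definite as all required. The protocol states neither.

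**2. Measure the overlap with the safety measures.**

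| Measure | Named in the Introduction as a manifestation of uveitis? |
|---|---|
| Ocular pain (Section 8.1.5) | Yes |
| BCVA | Yes, as blurry vision |
| Cells and flare (Sections 8.1.1, 8.1.2) | Yes |
| Slit-lamp signs in Table 3 | 1 of 6: conjunctival hyperemia. Not lid hyperemia, lid edema, chemosis, corneal edema or discharge |
| IOP | No. Raised IOP is attributed to ocular steroids; only glaucoma is listed, as a complication of uveitis |

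The overlap is real but partial.

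**3. Illustrate the possible size.** Up to 20 subjects at 1:1 gives n = 20/2 = 10 per arm. Let p be the true proportion of subjects with a drug-induced event, and q the share of those events rated Unrelated because uveitis could explain them. Both are assumptions, with subjects taken as independent. Then

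P(at least one related event in an arm) = 1 − [1 − p(1 − q)]^10, and the expected count is 10·p·(1 − q).

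For p = 20% and q = 50%: 1 − 0.90^10 = 65%, expected count 1.0.

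| p | q = 0 | q = 50% | q = 75% | q = 100% |
|---|---|---|---|---|
| 10% | 65% (1.0) | 40% (0.5) | 22% (0.25) | 0% (0) |
| 20% | 89% (2.0) | 65% (1.0) | 40% (0.5) | 0% (0) |
| 30% | 97% (3.0) | 80% (1.5) | 54% (0.75) | 0% (0) |

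Expected counts are in brackets.

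**The case against.** A reader might infer that every uveitis-like event must be rated Unrelated, so that drug-induced worsening is defined out of the result and a true 30% v 0% (3 of 10 v 0 of 10) is reported as 0% v 0%. The documents do not support that.

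- Whether uveitis easily explains an event is the investigator's judgement (Section 7.4). Hyperemia that goes from grade 1 to grade 3 with new pain days after the first drop could reasonably be judged not easily explained, and rated Probable. The 0% v 0% result needs q = 100%, which nothing in the documents implies.
- AEs are assessed 40 ± 10 minutes after the first dose (Appendix 1), which ties immediate irritation to dosing.

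A reader might also infer that all the main toxicity signals are covered, because Table 3 says "Safety parameters of interest include a change from baseline to each visit in ocular signs such as corneal/conjunctival tolerability", together with IOP. Part 2 above shows otherwise: one of six slit-lamp signs is named, and raised IOP is not. Cataract, glaucoma and macular edema are described as late results of untreated, recurrent disease, which is not an easy explanation for an acute event within 28 days of dosing.

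Nor are the events lost. Treatment-emergent AEs are listed by group whatever their causality, Section 7.2.1 promises separate summaries of ocular and non-ocular AEs, and slit-lamp findings, IOP and acuity are summarized (Section 9.1.2). Pain, cells and flare are compared descriptively between arms (Section 9.1.3). With about 20 subjects, 3 v 0 would be visible in a listing. That is a difference between doses, so the missing vehicle arm would not hide it.

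These points stand, and they limit the concern to the treatment-related result. They do not remove it: a listing does not correct a relatedness table, and the wording of the scale still departs from the reasonable-possibility standard.

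**Conclusion.** The concern holds for the treatment-related AE result. As worded, the scale permits an event with a plausible drug contribution to be rated Unrelated and, once uveitis is judged an easy explanation, closes the other two levels. This contradicts the reasonable-possibility definition in Section 7.3 and does not fit the possibly-related wording in Section 7.5. It can bias the treatment-related incidence downwards for events that resemble uveitis: pain, blurred vision, conjunctival hyperemia, cells and flare.

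The size cannot be estimated from the documents, which give neither event rates nor the share that would be so rated. The table in the working shows the range under stated assumptions and is not a prediction. The point justifies a wording change and one added table. It does not show that the trial would miss a safety signal.

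**What to change.** 1. **Narrow the uveitis ground under Unrelated** to events due wholly to uveitis, for example signs or symptoms present at Visit 1 and not worse since the first dose. State that a new or worsened study-eye event with a reasonable temporal relationship to dosing is not Unrelated solely because uveitis could explain it.
2. **Give such events a category.** Changing only the Probable condition that begins "Event cannot easily be explained by" is not enough. Probable also asks for a reaction that is likely to be known or is predicted by pharmacology, so a novel irritant effect could fit neither level. Either align all the Probable conditions or add a level that matches reasonable possibility, and bring Section 7.5 into line. Adding a level without step 1 would leave these events in Unrelated.
3. **Tabulate treatment-emergent AE incidence by arm regardless of causality**, beside the treatment-related table. Section 3.1 already names this incidence as part of the primary parameter.

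The cost is protocol and eCRF-guideline wording, plus one table. The downside is that temporal proximity exists for anyone dosing four times a day. Subjects also enter needing more steroid while otherwise on a stable regimen, so some ordinary flares will be counted as possibly related. The related-AE rate will rise by an amount the documents do not allow one to estimate. The causality-free table in step 3 lets a reader compare the arms without relying on that rating.
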